6.4 STUDY INTERVENTION COMPLIANCE

Using the paper form, "Daily Log for IP Intake", participants will keep a daily record of their assigned study drink intake, to both facilitate reconciliation and reduce recall bias when queried each week during phone assessment. The Clinical Trials Manager or a member of the study team will call participants on a weekly basis to assess, log, and track safety, tolerance and adherence to study drink consumption. An eCRF in the OnCore® system will be used to document and manage weekly data on each participant, regarding the number of doses missed per week and the reason(s) why. Compliance with study procedures will be assessed weekly for every participant. Participants will be in compliance if they receive at least one dose per day for an average of greater than 50% of study days.

6.5 CONCOMITANT THERAPY

Immediately prior to screening/baseline, participants' concomitant prescription medications, over-the-counter medications, and supplements are reviewed by the Clinical Trials Manager in Epic EMR (electronic medical record, Epic Systems Corporation) to verify exclusion criteria. Thereafter, at all visits and weekly telephone calls, participants are asked whether there have been any changes in their medications since their previous encounter with the Clinical Trials Manager or designee.

7 STUDY INTERVENTION DISCONTINUATION AND PARTICIPANT DISCONTINUATION/WITHDRAWAL

7.1 DISCONTINUATION OF STUDY INTERVENTION

A participant's elective discontinuation from soy or placebo intake means discontinuation from active participation in the study. Study personnel will attempt to collect any remaining study procedure data as the participant's (final) post-consumption data.

If a clinically significant finding is identified (including, but not limited to change in eligibility criteria from baseline) after enrollment, the Principal Investigator or qualified designee will determine if any change in participant management is needed. Any new clinically relevant finding will be reported as an adverse event (AE).

Data to be collected at the time of study intervention discontinuation will include data collected at date of study initiation (date of first participant enrollment) through to the date of last participant follow-up. Participants who withdraw prior to study termination will be discussed in the clinical study report. The trial database will be closed/frozen and be considered ready for final analysis after all queries and edits have been reviewed and applied.

No new health information will be gathered after the date of participant withdrawal/discontinuation. Information that has already been gathered may still be used until the end of the study, as necessary to insure the integrity of the study and/or study oversight.

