7.2 PARTICIPANT DISCONTINUATION/WITHDRAWAL FROM THE STUDY

Participants are free to withdraw from participation in the study at any time upon request.

Compliance with study requirements will be assessed throughout the study. Participants may be withdrawn from the study if they do not agree or adhere to study requirements listed in section 1.3, Schedule of Activities.

An investigator may discontinue or withdraw a participant from the study for the following reasons:

- Significant study intervention non-compliance
- Any clinical adverse event (AE), intercurrent illness, or other medical condition or situation occurs such that continued participation in the study would not be in the best interest of the participant
- Disease progression which requires discontinuation of the study intervention
- Development of any exclusion criteria (either newly developed or not previously recognized) that precludes further study participation
- Participant unable to consume fermented soy or placebo for 15 days.

The reason for participant discontinuation or withdrawal from the study will be recorded in the OnCore® electronic data capture system. Subjects who sign the informed consent form and are randomized but do not receive the study intervention may be replaced. Participants who sign the informed consent form, are randomized, and receive the study intervention, but either subsequently withdraw, or are withdrawn/discontinued from the study, will be replaced.

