9.3 POPULATIONS FOR ANALYSES

Intention-to-treat ('as randomized') analyses will be performed on all randomized participants. Duration of treatment will be taken into account in the analysis.

Per-protocol ('as-treated') analysis will also be carried out; assessment of treatment adherence will be based on self-reported reporting during phone follow-up calls.

The Safety Analysis dataset will include participants who took at least one dose of study medication.

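### Section 7.1 contradicts itself on data collection after a man stops the product; with mandatory replacement and no rule for a missing or early PSA, the as-randomized PSA analysis risks becoming a completers' analysis.

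*Protocol*

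**What the plan says.** Protocol section 7.1 makes three statements about a man who stops taking the product:

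- On his status: "elective discontinuation from soy or placebo intake means discontinuation from active participation in the study".
- On his data: "Study personnel will attempt to collect any remaining study procedure data as the participant's (final) post-consumption data".
- In the section's last paragraph: "No new health information will be gathered after the date of participant withdrawal/discontinuation".

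Section 7.2 lists reasons for which an investigator may withdraw a man. They include significant non-compliance and, as a separate item, "Participant unable to consume fermented soy or placebo for 15 days". On replacement, men who are "randomized but do not receive the study intervention may be replaced". For men who did receive product the rule is firmer: "but either subsequently withdraw, or are withdrawn/discontinued from the study, will be replaced".

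Section 9.3 states that intention-to-treat "analyses will be performed on all randomized participants". Sections 4.1, 6.3 and 9.4.8 also keep each man in his assigned group. The primary outcome in protocol section 9.4.2 and SAP section 1.1.2 is the change in PSA from baseline to admission for surgery. Neither document has a rule for a missing post-treatment PSA, and the SAP does not restate an analysis population.

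**The concern.** The primary comparison needs a PSA at admission from every randomized man. If the last paragraph of 7.1 is followed, a man who stops product has no such value. Whether the outcome exists then depends on whether he tolerated, or chose to keep taking, his assigned product. The active product has reported gastrointestinal effects (section 2.3.1), so loss could differ between arms.

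Replacement does not cure this. It restores the number of men with a PSA, but the added values come from other men. If PSA is not collected from those who stop, each arm's data come from men who stayed on product, although the analysis is labelled as-randomized.

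**Working it through.** **1. The statements in 7.1 side by side.** The attempt to collect remaining data can be read in two ways. It may mean a draw when the man stops, or it may mean the Visit 2 serology already in the schedule (section 1.3). The second reading delivers the primary endpoint, but the closing sentence of 7.1, which has no exception, forbids it once the man counts as discontinued. Section 8.1 does not settle the timing. It places the final blood draw both at admission for surgery and 24 hours after the last dose, and for a man who stops early these are different days. Section 8.1 does recognize that PSA remains obtainable when surgery is cancelled, but for men who continue dosing. No matching provision covers men who stop.

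**2. The plan's own sample size.** Inputs from section 9.2: difference 15, SD 20.3, power 0.80, two-sided alpha 0.05.

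- n per arm = 2 × (1.96 + 0.84)² × 20.3² / 15² = 28.8, so 29 per arm and 58 in total (30 per arm and 60 in total with the t distribution).
- The stated 72 is not reproduced. The excess might be an allowance for loss, but the protocol does not say so. That is a separate matter and neither supports nor weakens this point.

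**3. Loss of numbers is the smaller problem.** With 36 per arm, power by the normal approximation is 0.88. Without replacement, losing PSA in 5%, 10%, 20% or 30% of each arm gives 0.86, 0.84, 0.80 or 0.75. With replacement the count is restored, and selection remains.

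**4. Size of the selection effect.** Let d be the fraction of an arm without PSA, and s the amount by which their mean change differs from that of men with PSA. The mean over all randomized men equals the completers' mean plus d × s, so the completers' mean is off by d × s. The documents give neither d nor s for this trial. The nearest figure is the preliminary study in section 2.2, where 1 of 20 withdrew (5%). Taking s as one stated SD, and 20.3 as the SD of change:

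| Lost in one arm | Shift in that arm's mean | Share of the 15-unit target |
|---|---|---|
| 5% (1.8 of 36) | 0.05 × 20.3 = 1.0 | 1.0 / 15 = 7% |
| 11% (4 of 36) | 4/36 × 20.3 = 2.3 | 2.3 / 15 = 15% |

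If both arms lose men, the error in the between-arm difference is the gap in loss times s, when s is the same in both arms. It is zero when loss is equal. For 5% loss on placebo, 10% to 30% on the active product, and s of 10 to 20 units, it runs from (0.10 − 0.05) × 10 = 0.5 to (0.30 − 0.05) × 20 = 5.0 units. These rates are assumptions too.

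**5. The 15-day item and the compliance definition.** Section 6.4 reads: "Participants will be in compliance if they receive at least one dose per day for an average of greater than 50% of study days". A man who misses 15 days of a D-day course and otherwise takes at least one dose daily has dosed on (D − 15)/D of days. This exceeds 50% when D is above 30. At 28 days it is 13/28 = 46%; at 70 days it is 55/70 = 79%. So over most of the 4 to 10 week window a man can be compliant under 6.4 and still be open to withdrawal under 7.2.

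**The case against.** A reader might infer that the admission PSA is lost by rule and that the as-randomized analysis cannot be done. The documents do not go that far, for these reasons:

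- The sentence after the one on elective stopping plans an attempt to collect data, and this can mean the scheduled Visit 2 draw. Nothing says that the final sample is taken on the day of stopping. Loss is a risk created by conflicting text.
- The rule in 7.1 concerns elective stopping. Under section 6.1.2 a missed dose is logged and dosing resumes the next day, and withdrawal by the investigator under 7.2 is discretionary.
- Replacement does not by itself remove anyone from the analysis set. Section 9.3 still defines that set as all randomized men.
- A linear mixed model, one of the two primary methods named, can keep men who have only a baseline PSA, on the assumption that data are missing at random. The other named option, repeated measures ANOVA, ordinarily needs both values.
- The 15-day item and section 6.4 do not strictly contradict each other. One is a permitted reason for withdrawal and the other defines compliance, and a man can satisfy both.
- Evidence for differential loss is thin. The preliminary study had healthy adults, the liquid product and no placebo arm. Its one withdrawal has no stated reason. Its 3 + 1 + 1 + 4 = 9 gastrointestinal reports were mild and short-lasting, and are not linked to stopping or shown to come from nine people.

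All of this stands, and it limits the claim. It does not reconcile the two sentences in 7.1 or supply a rule for a missing or early PSA. Nor does the mixed model remove the bias if the men who stop differ in PSA change beyond what arm and baseline PSA predict.

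**Conclusion.** The point holds in this form. Section 7.1 gives incompatible instructions on data after stopping, section 7.2 makes replacement of treated men mandatory, and neither document covers a missing or early PSA. Together these put the promised as-randomized analysis at risk of becoming a completers' analysis; they do not make it impossible.

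The size cannot be fixed from the documents. The illustrative shift of 1.0 to 2.3 units in one arm's mean, 7% to 15% of the 15-unit target, assumes that 5% to 11% of that arm have no PSA and that their change differs by a full SD. The upper end is a deliberately unfavourable case. The SAP reports that the trial stopped short of its enrollment target, so each man without a PSA carries more weight than in an arm of 36.

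**What to change.** **Protocol, sections 7.1 and 7.2.**

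- Define stopping product and withdrawing consent as separate events.
- Seek the planned pre-surgery Visit 2 PSA from every randomized man who has not withdrawn consent for data collection.
- Limit the sentence that ends data gathering to withdrawal of consent.
- State that replaced men stay in the intention-to-treat set and that replacement only adds men.
- Clarify how the 15-day withdrawal reason relates to the compliance definition in 6.4. The choice of clinical rule stays with the investigator.

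**SAP and report.** Enrollment has ended, so new wording cannot recover draws that were missed. The SAP should define the analysis set and say how a PSA taken at stopping is treated. The report should account for every randomized man by arm, including those replaced, and give the PSA timing for those who stopped. A missing-data sensitivity analysis should be added, for example one that shifts the unobserved changes over a stated range in each arm.

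**Cost.** Amendment wording and a short addition to the SAP and report, with no new visit or test. The small downside is that the estimate will include men who took little product.

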7.2 PARTICIPANT DISCONTINUATION/WITHDRAWAL FROM THE STUDY

Participants are free to withdraw from participation in the study at any time upon request.

Compliance with study requirements will be assessed throughout the study. Participants may be withdrawn from the study if they do not agree or adhere to study requirements listed in section 1.3, Schedule of Activities.

An investigator may discontinue or withdraw a participant from the study for the following reasons:

- Significant study intervention non-compliance
- Any clinical adverse event (AE), intercurrent illness, or other medical condition or situation occurs such that continued participation in the study would not be in the best interest of the participant
- Disease progression which requires discontinuation of the study intervention
- Development of any exclusion criteria (either newly developed or not previously recognized) that precludes further study participation
- Participant unable to consume fermented soy or placebo for 15 days.

The reason for participant discontinuation or withdrawal from the study will be recorded in the OnCore® electronic data capture system. Subjects who sign the informed consent form and are randomized but do not receive the study intervention may be replaced. Participants who sign the informed consent form, are randomized, and receive the study intervention, but either subsequently withdraw, or are withdrawn/discontinued from the study, will be replaced.

7.3 LOST TO FOLLOW-UP

A participant will be considered lost to follow-up if he fails to return for Visit 1 or Visit 2 and is unable to be contacted by study staff.

The following actions will be taken if a participant fails to return to the clinic for a required study visit:

- Study staff will attempt to contact the participant the day the appointment was missed to reschedule the missed visit as soon as possible, and will counsel the participant on the importance of maintaining the assigned visit schedule and ascertain if the participant wishes to and/or should continue in the study.

- Before a participant is deemed lost to follow-up, the investigator or clinical trials manager will make every effort to regain contact with the participant (where possible, 3 telephone calls and email attempts). These contact attempts will be documented in the participant's study file.
- Should the participant continue to be unreachable, he will be considered to have withdrawn from the study with a primary reason noted and date of lost to follow-up recorded in the participant's study file and in OnCore®.

8 STUDY ASSESSMENTS AND PROCEDURES

8.1 EFFICACY ASSESSMENTS

Sequence of events to occur during the screening process and any decision points regarding participant eligibility: Positive post-biopsy prostate cancer patients of the PI and other Yale School of Medicine referring urologists will be invited to participate in the study. The patients will be identified to the clinical trials manager, who will invite them to meet in person for clinical screening at the Yale Center for Clinical Investigation's outpatient research clinic, the CSRU (Church Street Research Unit), or LMH's or SCH's urology clinic area (determined by referring physician's location), as they await prostatectomy. An initial phone screening will take place to first, to assess the patient's interest in participating, discuss study details, and determine whether any unknown exclusion criteria exist before scheduling the screening visit. The referring urologist determines their patients' eligibility for study entry at time of referral.

Time frame prior to enrollment within which screening procedures/evaluations must be performed: The Screening/Baseline Visit will take place as soon after the patient's prostatic biopsy as possible. Ideally, study enrollment will occur within 3-4 days after the Screening/Baseline Visit, as patients will have been given their date for prostatectomy, and the interim between biopsy and surgery is the period of the intervention.

In the event a randomized patient's prostatectomy is postponed (whether by patient preference or otherwise) beyond 180 days from the initial Screening/Baseline visit, the patient must be re-screened to have new baseline laboratory values established if he wishes to resume participation in the study.

Procedures and evaluations to be done as part of the study to support the determination of efficacy include:

- **Biological specimen collection and laboratory evaluations** – Screening/baseline and end-of-study serology (final study visit, Visit 2 - time of admission for surgery, 24 hours after ingestion of the last study dose) includes:

PHI (prostate health index, which gives total and % free PSA - prostate-specific antigen), ESR (erythrocyte sedimentation rate), CBC with Diff (complete blood count with differential), CMP (comprehensive metabolic panel), testosterone (total, bioavailable and free), CRP (C-reactive protein), lipase, lipid panel, amylase, TSH (thyroid stimulating hormone), estrogen, IGF-1 (insulin-like growth factor), IGFBP-1, IGFBP-2, and IGFBP-3 (insulin-like growth factor binding proteins).

- Nursing staff and phlebotomists at all sites are trained and certified in standard phlebotomy techniques.
- Total volume of blood to be drawn per subject visit is approximately 20-30 cc.

- A single, central processing laboratory (YNHH) will be used for all sites, to decrease variability in test results for the primary outcome, PSA.
- ***Special assays or procedures required*** – The following pathological analyses and assays will be performed after the study has closed to enrollment:
 - Pathological investigation of the removed prostate gland, analyzing any modulation of prostate cancer grade (Gleason score) and disease progression (CAPRA-S) compared to preoperative biopsies, volume of gland and of biopsy-proven, index prostate cancer lesion, and extent (involvement of surgical margins and extraprostatic extension) of clinical and pathological tumor stage and degree of tumor focality.
 - Telomere length (*TeloTAGGG™ Telomere Length Assay*) will be used to estimate telomeric DNA length from prostate cancer tissue.
 - Automated quantitative (AQUA) immunofluorescence analysis of markers of prostate cancer aggressiveness on a tissue microarray, using fluorescent tags to define tumors, localize sub-cellular compartments, and grade intensity of specific markers.
- ***Instances when curative treatment plan changes*** – Should an enrolled participant's course of treatment change in that he would not undergo prostatectomy (such as undergoing radiation therapy instead), with the treating urologist's approval, the participant may elect to remain in the study, continue daily IP dosing and attend his final subject visit as scheduled. The primary outcome of the study is prostate-specific antigen (PSA), which can be obtained post-IP consumption regardless. It is accepted that the secondary outcomes (AQUA, CCP and telomere assay) comparing biopsied tissue with tissue from the resectioned prostate would be lost in these rare instances when individuals do not undergo surgical removal of their prostate.
- ***Administration of questionnaires, instruments and patient-reported outcomes*** - Participants will be asked to complete:
 - An inventory of soy-containing foods they have consumed within the past month at Screening/Baseline.
 - Pre/post FACT-P (Functional Assessment of Cancer Therapy - Prostate), a validated, 39-item questionnaire that measures health-related quality of life specific to men with prostate cancer, and assesses well-being in four domains (physical, social/family, emotional, and functional).
 - Participants will be given thorough dosing instructions for consuming the study drink, and will be asked to complete a daily dosing diary.

Follow-up procedures after administration: The final participant assessments will occur at Visit 2, approximately 24-48 hours prior to prostatectomy. No further follow-up by research personnel is planned at this time; patients will be followed by their treating urologist for clinical care.

8.2 SAFETY AND OTHER ASSESSMENTS

Sequence of events to occur during the screening process and any decision points regarding participant eligibility: refer to Section 8.1, Efficacy Assessments

Time frame prior to enrollment within which screening procedures/evaluations must be performed: refer to Section 8.1, Efficacy Assessments

Procedures and evaluations to be done as part of the study to support the determination of safety include:

- **Biological specimen collection and laboratory evaluations -**
 - Screening/Baseline Serology (to ensure patients' laboratory results are within acceptable range for study participation): CRP (C-reactive protein), lipase, lipid panel, amylase, TSH (thyroid stimulating hormone), ESR (erythrocyte sedimentation rate), CBC with Diff (complete blood count with differential), and CMP (comprehensive metabolic panel). These tests will be repeated at Visit 2 to ensure deleterious changes have not occurred and that patients' laboratory results are within acceptable range prior to prostatectomy (refer to Section 1.3, SOA for complete serology list).
 - Nursing staff and phlebotomists at all sites are trained and certified in standard phlebotomy techniques.
 - Total volume of blood to be drawn at Screening/Baseline and at Visit 2 is approximately 20-30 cc.
- **Administration of questionnaires, instruments and patient-reported outcomes** – refer to Section 8.1, Efficacy Assessments
- **Counseling procedures, including any dietary or activity considerations** - During this study, participants may maintain their current diet and level of physical activity to which they are accustomed, i.e., they will not be asked to abstain from small amounts of soy in their diet. (At time of phone screening, individuals who reported current high-dose soy consumption, use of herbal supplements, or soy or vegetarian nutrition, or any other extreme dietary habits – or soy allergy or sensitivity – would have been excluded from participation.) Participants will be given thorough dosing instructions for consuming the study drink, and will be asked to complete a daily dosing diary.
- **Assessment of study intervention adherence** - Safety, tolerability and adherence to IP intake will be assessed through participant self-report since baseline, via weekly phone calls to participants until they complete the study (Visit 2). If any AEs are noted during the phone assessments or study visits, they will also be recorded in OnCore® using an Adverse Events eCRF, including actions taken to resolve the AE.

